12.3.2 Background Characteristics

Subject disposition, demographic and baseline characteristics, prior and concomitant medications, study drug exposure and compliance, and other background characteristics will be summarized. Additionally, all subject data will be presented in subject data listings. All

summaries will be based on the FAS unless otherwise specified in the SAP for the study. No statistical hypothesis testing will be performed on background characteristics.

12.3.2.1 Subject Disposition

Number and percentage of subjects in the following categories will be summarized by treatment sequence:

- All Subjects Set
- All Randomized
- Safety Set
- FAS: Subjects who are randomized and dosed and carry the intended *CFTR* mutations (see [Section 16](#))

The number and percentage (based on the FAS) of subjects in each of the following disposition categories will be presented:

- Completed study drug treatment
- Prematurely discontinued study drug treatment and the reasons for discontinuation
- Last scheduled on-treatment visit completed for subjects who discontinued study drug treatment
- Completed study
- Prematurely discontinued the study and the reasons for discontinuation
- Prematurely discontinued the study during the Treatment Period and the reasons for discontinuation
- Last scheduled visit completed
- Rolled over to extension study

12.3.2.2 Demographics and Baseline Characteristics

Demographic, background (e.g., medical history), and baseline characteristics will be summarized by treatment sequence. Protocol deviations/violations will be provided as a subject data listing only. Important protocol deviations/violations will be summarized.

The following demographics and study baseline characteristics will be summarized by treatment sequence for the FAS: sex, race, ethnicity, age, weight, height, body mass index (BMI), region, study baseline percent predicted FEV₁, study baseline sweat chloride, and study baseline score of CFQ-R respiratory domain.

12.3.2.3 Prior and Concomitant Medications

Medications used in this study will be coded by using the World Health Organization Drug Dictionary Enhanced and categorized as follows:

- **Prior medication:** any medication that started before the first dose of study drug, regardless of when it ended.
- **Concomitant medication:** medication continued or newly received during the TE period for Treatment Period 1 or Treatment Period 2. If a subject took a medication during a specific Treatment Period, this medication will be attributed to the treatment the subject received during this Treatment Period. As a result, 1 medication could be attributed to more than 1 treatment.
- **Post-treatment medication:** medication continued or newly received beyond the TE period for Treatment Period 2, or between the TE periods for Treatment Period 1 and Treatment Period 2, or beyond the TE period for Treatment Period 1 for subjects who do not participate in Treatment Period 2.

A given medication can be classified as a prior medication, a concomitant medication, or a post-treatment medication; both prior and concomitant; both concomitant and post-treatment; or prior, concomitant, and post-treatment. If a medication has a missing or partial missing start/end date or time and it cannot be determined whether the medication was taken before initial dosing, concomitantly, or post-treatment, it will be considered as prior, concomitant, and post-treatment.

Prior medications will be summarized by treatment sequence, and concomitant medications will be summarized by treatment based on the FAS. Post-treatment medications will be listed for each subject.

12.3.2.4 Study Drug Exposure and Compliance

Exposure to study drug (i.e., duration of treatment) will be summarized by treatment for the FAS in terms of duration of treatment a subject received (in days), defined as the last day minus the first day of study drug plus 1 within the Treatment Period.

Study drug compliance will be calculated as follows:

$$100 \times [1 - (\text{Total number of days study drug interrupted}) / (\text{Duration of study drug exposure})].$$

The total number of days of study drug interrupted is defined as the sum of (number of days of study drug interrupted in each interruption interval); where number of days of study drug interrupted in each interval is defined as the interruption end date - the corresponding interruption start date + 1.

Duration of treatment and study drug compliance will be summarized by means of descriptive summary statistics.

12.3.3 Efficacy Analysis

The primary objective of this study is to evaluate the efficacy of VX-661/ivacaftor and ivacaftor monotherapy. For efficacy analysis, the statistical inference will be based on change from study baseline. A hierarchical testing strategy will be used to preserve the overall type I error rate at the 0.05 level.

12.3.3.1 Analysis of Primary Variables

The primary efficacy endpoint is the absolute change in percent predicted FEV₁ from study baseline to the average of the Week 4 and Week 8 measurements of each of the Treatment Periods. The null hypotheses to be tested are that the mean change from study baseline in percent predicted FEV₁ to the average of the Week 4 and Week 8 measurements is the same for (i) VX-661/ivacaftor and placebo and (ii) ivacaftor monotherapy and placebo.

The primary efficacy analysis is based on a mixed effects model. This model will include the absolute change from study baseline in percent predicted FEV₁ to the average of the Week 4 and Week 8 measurements as the dependent variable, treatment and period as fixed effects, and subject as a random effect. The within-subject covariance will be assumed to have the same compound symmetry (CS) structure for sequences containing placebo treatment but will be different from the CS structure for sequences containing active treatment in both periods. Denominator degrees of freedom for the F-test for fixed effects will be estimated using the Kenward-Roger approximation.⁵¹ No imputation of missing data will be done. Subjects who have data only for one of the periods will have a structure similar to a parallel group trial. Assuming that the subjects have dropped out at random, an estimate of treatment effect will be based on such subjects and will then be combined with the estimate from subjects who have data in both Treatment Periods with weights based on the precision of these estimates.

The estimated mean of the dependent variable, a 95% confidence interval, and a 2-sided *P* value will be provided for each treatment. Similarly, the estimated between group treatment differences along with the corresponding 95% confidence interval and 2-sided *P* values will be presented. A sensitivity analysis based on a mixed effects model using absolute change from study baseline in percent predicted FEV₁ to the average of the Week 4 and Week 8 measurements of Treatment Period 1 will be performed to assess the treatment difference as compared to the primary efficacy analysis. The resulting model will include treatment as a fixed effect, study baseline as covariate and subject as a random effect. Additionally, a mixed model repeated measures (MMRM) will be used with period, visit, treatment, and treatment by visit as fixed effects and subject as a random effect. The change from study baseline will be the dependent variable. The repeated measures analysis will enable usage of all post-baseline available data and provide least squares mean estimates at each visit within a given treatment as well as estimates of treatment difference at each visit or across all visits.

12.3.3.2 Analysis of Secondary Efficacy Variables

For all secondary efficacy endpoints, the primary analysis will be based on change from study baseline.

Key Secondary Endpoint

- **Absolute change in the CFQ-R respiratory domain score from study baseline to the average of the Week 4 and Week 8 measurements in each Treatment Period:**
Analysis of this variable will be similar to that of the primary analysis of the primary efficacy endpoint.

Secondary Endpoints

[figure not shown]
- **Relative change in percent predicted FEV₁ from study baseline to the average of the Week 4 and Week 8 measurements of each of the Treatment Periods:** Analysis of this variable will be similar to that of the primary analysis of the primary efficacy endpoint.
- **Absolute change in sweat chloride from study baseline to the average of the Week 4 and Week 8 measurements in each Treatment Period:** Analysis of this variable will be similar to that of the primary analysis of the primary efficacy endpoint.

Sensitivity analysis, supportive analysis, and subgroup analysis of secondary variables may be described in the SAP.

12.3.3.3 Adjustment for Multiple Comparisons

There are 3 potential treatment comparisons for the primary and key secondary endpoint: VX-661/ivacaftor versus placebo, ivacaftor monotherapy versus placebo, and VX-661/ivacaftor versus ivacaftor monotherapy. The testing strategy will be limited to the comparison of VX-661/ivacaftor versus placebo and ivacaftor monotherapy versus placebo. The testing procedure is summarized in [Figure 12-1](#).

Figure 12-1 Testing Strategy for the Primary and Key Secondary Endpoint

IVA: ivacaftor; PBO: placebo; ppFEV₁: percent predicted forced expiratory volume in 1 second;
CFQ-R: Cystic Fibrosis Questionnaire–Revised (respiratory domain)

A hierarchical testing strategy with $\alpha = 0.05$ will be used to strongly control the overall type I error rate at the 0.05 level. The testing hierarchy is as follows:

1. Absolute change in percent predicted FEV₁ from study baseline to the average of the Week 4 and Week 8 measurements for VX-661/ivacaftor versus placebo.
2. Absolute change in percent predicted FEV₁ from study baseline to the average of the Week 4 and Week 8 measurements for ivacaftor monotherapy versus placebo.
3. Absolute change in CFQ-R respiratory domain score from study baseline to the average of the Week 4 and Week 8 measurements for VX-661/ivacaftor versus placebo.
4. Absolute change in CFQ-R respiratory domain score from study baseline to the average of the Week 4 and Week 8 measurements for ivacaftor monotherapy versus placebo.

Note that comparisons of VX-661/ivacaftor versus ivacaftor will be performed and the *P*-values will be reported, but the tests will be performed without strong Type I error control.

12.3.4 Safety Analysis

All safety analyses will be based on the set of data associated with the TE period for Treatment Period 1 and the TE period for Treatment Period 2. Safety analyses will use the Safety Set. The summaries will be by treatment received.

For safety analysis, the period baseline will be used.

All safety data will be presented in individual subject data listings.

The overall safety profile of study drug will be assessed in terms of the following safety and tolerability endpoints:

- Incidence of treatment-emergent adverse events (TEAEs)
- Clinical laboratory values (i.e., hematology, serum chemistry, lipid panel, vitamin levels, urinalysis, and coagulation studies)
- ECGs
- Vital signs
- Pulse oximetry
- Spirometry

12.3.4.1 Adverse Events

For analysis purposes, AEs will be classified as pretreatment AEs, TEAEs, or post-treatment AEs, defined as follows:

- **Pretreatment AE:** any AE that started before the first dose of study drug.
- **TEAE:** any AE that increased in severity or that was newly developed during the TE period for Treatment Period 1 or Treatment Period 2. An AE that started (or increased in severity) during a specific Treatment Period will be attributed to the treatment the subject was receiving during the Treatment Period.
- **Post-treatment AE:** any AE that increased in severity or that was newly developed beyond the TE period for Treatment Period 2, or between the TE periods for Treatment Period 1 and Treatment Period 2, or beyond the TE period for Treatment Period 1 for subjects who do not have Treatment Period 2.

For AEs with missing or partial start date, if there is no clear evidence that the AEs started (or increased in severity) before the first dose, the start date will be imputed to the first dosing date and the AE assigned to the treatment in Treatment Period 1.

AE summary tables will be presented for TEAE only and will include the following:

- All TEAEs
- TEAEs by relationship
- TEAEs by maximal severity
- TEAEs leading to treatment discontinuation

- Serious TEAEs
- TEAEs leading to death
- Frequently reported TEAEs

Summaries will be presented by MedDRA system organ class and preferred term using frequency counts and percentages (i.e., number and percentage of subjects with an event). When summarizing the number and percentage of subjects with an event, subjects with multiple occurrences of the same AE or a continuing AE will be counted once, only the maximum severity level will be presented in the severity summaries, and the worst/highest relationship level in the relationship summaries. An AE overview table will be provided. In addition, a listing containing individual subject AE data for all deaths and other serious and significant AEs will be provided separately. All AEs, including pre- and post-treatment AEs, will be presented in individual subject data listings.

12.3.4.2 Clinical Laboratory Assessments

The raw values and change from period baseline values of the continuous laboratory parameters will be summarized in SI units by treatment group at each scheduled time point during the TE period. In addition, the mean value at each visit will be plotted by treatment groups for each of the liver function parameters.

The number and percentage of subjects with at least 1 potentially clinically significant (PCS) event during the TE period will be summarized by treatment group. The PCS (post-baseline) shift from period baseline will also be summarized by treatment group for selected laboratory parameters. The PCS criteria and the parameter selection criteria will be provided in the SAP.

Results of urinalysis and serum pregnancy test will be listed in individual subject data listings only. In addition, a listing containing individual subject laboratory measurements outside the reference ranges will be provided. This listing will include data from scheduled and unscheduled time points.

12.3.4.3 Electrocardiogram

A summary of raw values and change from period baseline values will be provided by treatment group at each scheduled time point during the TE period for the following standard digital ECG measurements: PR, QT, and QTc for HR interval (QTcF); QRS duration; and HR. In addition, the mean value at each visit will be plotted by treatment groups for QTcF.

The number and percentage of subjects with at least 1 PCS event during the TE period will be tabulated by treatment group. The PCS criteria for ECG data will be provided in the SAP.

Additional ECG analyses will be described in the SAP.

12.3.4.4 Vital Signs

The raw values and change from period baseline values during the TE period will be summarized by treatment group at each scheduled time point: systolic and diastolic blood pressure (mm Hg), body temperature (°C), HR (beats per minute [bpm]), and respiratory rate (breaths per minute).

The number and percentage of subjects with at least 1 PCS event during the TE period will be tabulated by treatment group. The PCS criteria for vital signs data will be provided in the SAP.

Additional vital sign analyses will be described in the SAP.

12.3.4.5 Physical Examination

PE findings will be presented as a data listing only. Clinically relevant results identified after screening will be reported as AEs.

12.3.4.6 Other Safety Analysis

12.3.4.6.1 Pulse Oximetry

A summary of raw values and change from period baseline values during the TE period will be provided by treatment groups at each scheduled time point for the percent of oxygen saturation by pulse oximetry. In addition, the mean value at each visit will be plotted by treatment group for the percent of oxygen saturation.

The number and percentage of subjects with shift changes from period baseline (normal/missing and low according to the reference range) to the lowest percent of oxygen saturation during the TE period will be tabulated by treatment group.

12.3.4.6.2 Postdose Spirometry

For the 2-hour and 4-hour postdose measurements on Day 1 of each Treatment Period (Week 1 and Week 17), and at Day 15 of each Treatment Period (Week 2 and Week 18), a summary of raw values for percent predicted FEV₁ will be provided by treatment at each time point. The absolute change from the predose value of percent predicted FEV₁ on the same day will be summarized by treatment at each time point. In addition, a boxplot by time point will be provided. Within each treatment, Day 1 and Day 15 values will be presented on the same plot.

The above analyses will be repeated for FEV₁.

In addition, the number and percentage of subjects with percent predicted FEV₁ decline ≥ 10 , ≥ 15 , and ≥ 20 percentage points in the absolute change from the predose value will be summarized by treatment and by assessment day and time.

12.3.5 Interim and IDMC Analyses

12.3.5.1 Interim Analysis

No interim analyses of efficacy are planned.

12.3.5.2 IDMC Analysis

An IDMC will be formed before study initiation. The IDMC's objectives and operational details will be defined in a separate document (IDMC Charter), which will be finalized before the first subject is screened. The IDMC will conduct regular planned safety reviews of study data as outlined in the IDMC Charter.

12.4 Clinical Pharmacology Analysis

A detailed description of the clinical pharmacology analyses will be provided in a CPAP. Listings of plasma concentration data of VX-661, ivacaftor, and their metabolites will be provided in the clinical study report. A population approach will be used to analyze the time-versus-plasma concentration data of VX-661, ivacaftor, and their metabolites. The PK/PD relationship between concentrations of VX-661 and ivacaftor and (their metabolites as appropriate) and efficacy and safety measurements may be investigated. The results of the PK and PK/PD analyses using a population approach will be presented in a separate report.

13 PROCEDURAL, ETHICAL, REGULATORY, AND ADMINISTRATIVE CONSIDERATIONS

13.1 Adverse Event and Serious Adverse Event Documentation, Severity Grading, and Reporting

13.1.1 Adverse Events

13.1.1.1 Definition of an Adverse Event

An AE is defined as any untoward medical occurrence in a subject during the study; the event does not necessarily have a causal relationship with the treatment. This includes any newly occurring event or worsening of a preexisting condition (e.g., increase in its severity or frequency) after the ICF is signed.

An AE is considered serious if it meets the definition in [Section 13.1.2.1](#).

13.1.1.2 Clinically Significant Assessments

Study assessments, including laboratory tests, ECGs, PEs, and vital signs, will be assessed, and those deemed a clinically significant worsening from baseline documented as an AE. When possible, a clinical diagnosis for the study assessment will be provided rather than the abnormal test result alone (e.g., urinary tract infection, anemia). In the absence of a diagnosis, the abnormal study assessment itself will be listed as the AE (e.g., bacteria in urine or decreased hemoglobin).

An abnormal study assessment is considered clinically significant if the subject has 1 or more of the following:

- Concomitant signs or symptoms related to the abnormal study assessment
- Further diagnostic testing or medical/surgical intervention
- A change in the dose of study drug or discontinuation from the study

Repeat testing to determine whether the result is abnormal, in the absence of any of the above criteria, does not necessarily meet clinically significant criteria. The determination of whether the study assessment results are clinically significant will be made by the investigator.

A laboratory value that is Grade 4 will not automatically be an SAE. A Grade 4 laboratory value will be an SAE if the clinical status of the subject indicates a life-threatening AE.

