8.1.6 Early Treatment Termination

If the subject prematurely discontinues study drug treatment or is withdrawn from the study, an Early Treatment Termination (ETT) Visit should be scheduled as soon as possible after the last dose of study drug. Such subjects will also be required to complete the Safety Follow-up Visit, approximately 28 days \pm 7 days after their last dose of study drug. The assessments performed at the Safety Follow-up Visit are listed in [Table 3-2](#).

If the ETT Visit occurs 3 weeks or later following the last dose of study drug, then the ETT Visit will replace the Safety Follow-up Visit, and a separate Safety Follow-up Visit will not be required.

Subjects who prematurely discontinue study drug treatment will continue to complete all other scheduled study visits for assessments of efficacy (spirometry, sweat chloride, and CFQ-R) and [REDACTED]

[REDACTED] through the end of the Treatment Period in which discontinuation occurred, as detailed in the Schedule of Assessments ([Section 3](#)).

If the subject withdraws from the study and also withdraws consent for disclosure of future information, no further evaluations will be performed, and no additional data will be

collected. Vertex may retain and continue to use any data collected before such withdrawal of consent.

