10.4 Dose Modification for Toxicity

The dosage of individual study drugs or the regimen cannot be altered, but the investigator can interrupt or stop treatment with all study drugs.

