11.7.2 Clinical Laboratory Assessments

Blood and urine samples will be analyzed at a central laboratory, with the exception of urine pregnancy tests, which will be performed and analyzed at the site. Blood samples requiring a 4-hour fast will be collected on Day 1, Week 8, Week 17, Week 24, and the ETT Visit. Fasting is not required at other time points unless specified in the assessment table. On Day 1 and Week 17 Visit, blood samples will be collected before the first dose of the study drug. At all the other scheduled visits, these samples will be collected at any time during the visit, relative to the order of assessments indicated in [Section 11.1](#) and according to the schedule in [Table 3-1](#) and [Table 3-2](#).

Blood and urine samples for clinical laboratory assessments will be collected as shown in [Table 3-1](#) and [Table 3-2](#). Laboratory test results that are abnormal and considered clinically significant will be reported as AEs (see [Section 13.1.1](#)).

The safety laboratory test panels are shown in [Table 11-1](#).

Table 11-1 Safety Laboratory Test Panels

Serum Chemistry	Hematology	Urinalysis ^a
Glucose	Hemoglobin	Leukocyte esterase
Blood urea nitrogen	Erythrocytes	Nitrite
Creatinine	Mean corpuscular hemoglobin	Urobilinogen
Sodium	Mean corpuscular hemoglobin concentration	Urine protein
Potassium	Mean corpuscular volume	pH
Calcium	Reticulocytes	Urine blood
Chloride	Platelets	Specific gravity
Magnesium	Leukocytes	Urine ketones
Bicarbonate	Differential (absolute and percent):	Urine bilirubin
Inorganic phosphate	Eosinophils	Urine glucose
Total bilirubin, direct bilirubin	Basophils	
Alkaline phosphatase	Neutrophils	
Aspartate aminotransferase	Lymphocytes	
Alanine aminotransferase	Monocytes	
Lactate dehydrogenase	Coagulation Studies	
Gamma-glutamyl transpeptidase	Activated partial thromboplastin time	
Total protein	Prothrombin time	
Albumin	Prothrombin time International Normalized Ratio	
Creatine kinase		
Amylase		
Lipase		
Vitamin Levels		
Vitamins A, D, E, K, and B12		
Lipid Panel		
Total cholesterol		
Triglycerides		
Low-density lipoprotein		
High-density lipoprotein		

^a If urine is positive for leukocyte esterase, nitrite, protein, or blood, microscopic examination of urine will be performed for leukocytes, erythrocytes, crystals, bacteria, and casts.

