13.1.1.3 Documentation of Adverse Events

All AEs will be collected from the time ICF is signed until the following time points:

- For subjects who do not enroll: until time of screen failure (e.g., screen failure, withdrawal of consent)
- For enrolled subjects who have a Safety Follow-up Visit: through the Safety Follow-up Visit
- For enrolled subjects who do not have a Safety Follow-up Visit, through the **earliest** of
 - 28 days after the last dose of study drug
 - The ETT Visit, if that visit is 3 weeks or later following the last dose of study drug ([Section 8.1.6](#))
 - prior to the first dose of study drug in the extension study.

All subjects will be queried, using non-leading questions, about the occurrence of AEs at each study visit. When possible, a constellation of signs and/or symptoms will be identified as 1 overall event or diagnosis. All AEs for enrolled subjects will be recorded in the eCRF and source document. AEs for subjects who are screened but not subsequently enrolled in the study will be recorded only in the subject's source documents. The following data will be documented for each AE:

- Description of the event
- Classification of “serious” or “nonserious”
- Date of first occurrence and date of resolution (if applicable)
- Severity
- Causal relationship to study drug(s)
- Action taken
- Outcome
- Concomitant medication or other treatment given
- Indication of dose limiting toxicity

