13.1.1.6 Study Drug Action Taken

The investigator will classify the study drug action taken with regard to the AE. The action taken will be classified according to the categories shown in Table 13-3.

Table 13-3 Classifications for Study Drug Action Taken With Regard to an AE

Classification	Definition
Dose not changed	Study drug dose not changed in response to an AE.
Dose reduced	Not applicable for this study
Drug interrupted	Study drug administration interrupted in response to an AE.
Drug withdrawn	Study drug administration permanently discontinued in response to an AE.
Not applicable	Action taken regarding study drug administration does not apply. "Not applicable" will be used in circumstances such as when the investigational treatment had been completed before the AE began and no opportunity to decide whether to continue, interrupt, or withdraw treatment is possible.

AE: adverse event.

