#### 8.4.1.1 Overview of Treatment Emergent AEs

An overview of all TEAEs will be summarized in the following categories:

- Any TEAEs
- TEAEs by relationship
- Related TEAEs
- TEAEs by severity
- Grade 3/4 TEAEs
- Serious TEAEs
- Related Serious TEAEs
- TEAEs leading to treatment discontinuation (this will include TEAEs leading to discontinuation of either TEZ/IVA tablet or the IVA tablet)
- TEAEs leading to treatment interruption (this will include TEAEs leading to interruption of either TEZ/IVA tablet or the IVA tablet)
- TEAEs leading to death

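### The AE-reporting criterion for abnormal results names a dose change, which this trial does not allow, and omits interruption and permanent discontinuation of study drug

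*Protocol*

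**What the plan says.** Protocol 13.1.1.2 records an abnormal assessment as an AE when it is a clinically significant worsening. Section 11.7.2 repeats this for laboratory tests: "Laboratory test results that are abnormal and considered clinically significant will be reported as AEs". Sections 11.7.3 and 11.7.4 do the same for physical examinations and ECGs.

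Section 13.1.1.2 lists three criteria, any one of which makes a result clinically significant: related signs or symptoms; further diagnostic work or an intervention; and "A change in the dose of study drug or discontinuation from the study". It adds that repeating a test to see whether a result is truly abnormal does not necessarily qualify, and it leaves the determination to the investigator.

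On dosing, Protocol 10.4 says: "The dosage of individual study drugs or the regimen cannot be altered, but the investigator can interrupt or stop treatment with all study drugs". Table 13-3 in 13.1.1.6 marks the dose-reduced category "Not applicable for this study" and keeps interruption as a category of its own: "Study drug administration interrupted in response to an AE". On follow-up, 8.1.6 says: "Subjects who prematurely discontinue study drug treatment will continue to complete all other scheduled study visits".

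SAP 8.4.1.1 counts "TEAEs leading to treatment interruption (this will include TEAEs leading to interruption of either TEZ/IVA tablet or the IVA tablet", with a matching line for discontinuation. SAP 8.4.1.9 adds summaries by system organ class and preferred term, and listings, for both.

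**The concern.** The third criterion reads as if written for a trial with dose adjustment, in which stopping drug means leaving the study. Neither holds here. A site that works through the three criteria finds nothing to say that holding or stopping study drug because of an abnormal result makes that result reportable.

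What is at stake is the completeness of two tolerability outputs. Action taken is a field of the AE record (13.1.1.3, 13.1.1.6), and the SAP counts interruptions and discontinuations for safety through TEAEs. If no AE is recorded, the dosing action has nothing to attach to. Safety of both active regimens is a secondary objective (Protocol 6.2), so these tables matter even though no test depends on them.

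**Working it through.** The plan gives no figure to reproduce; the check is textual.

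**Step 1. Compare the possible dosing actions with the third criterion.**

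| Action | Possible here? | Named in the third criterion? |
|---|---|---|
| Dose change | No (10.4; Table 13-3) | Yes |
| Interruption of study drug | Yes (10.4, 10.5; Table 13-3) | No |
| Permanent discontinuation of study drug | Yes (10.4, 9.5; Table 13-3) | No |
| Leaving the study | Yes, but distinct from stopping drug (8.1.6, 9.5) | Yes |

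Reading a dose change loosely, so that it covers a hold, does not work. Table 13-3 treats dose reduction, interruption and withdrawal as separate categories.

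**Step 2. Follow one case.** A subject has a raised creatine kinase or lipase without symptoms. The test is repeated, the value is confirmed, and the investigator holds study drug.

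- Criterion 1 (signs or symptoms): not met.
- Criterion 2 (further diagnostic work or intervention): not clearly met, because a confirmatory repeat does not necessarily count.
- Criterion 3: not met. The dose was not changed and the subject is still in the study.

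The result becomes an AE only if the investigator independently calls it clinically significant. No other section of the protocol requires an abnormal result that led to a hold or stop to be recorded as an AE.

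**Step 3. Trace it through the SAP if no AE is recorded.**

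- TEAE-leading-to-interruption and TEAE-leading-to-discontinuation summaries and listings (SAP 8.4.1.1, 8.4.1.9): absent.
- Disposition (SAP 8.2.1): a discontinuation appears with its reason; an interruption does not appear.
- Compliance rate (SAP 8.2.6): an interruption contributes its days, without a reason.
- Laboratory and ECG threshold tables (SAP 8.4.2, 8.4.3) and the listing of elevated liver tests: the value appears, without a link to the dosing action.

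Discontinuations therefore have a partial backstop. In the specified summaries, interruptions survive only as days in the compliance rate.

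**Step 4. Scale of one event.** Each treatment occurs in 4 of the 6 sequences. At 34 subjects per sequence that is 34 × 4 = 136 planned subject-periods per treatment, so one unrecorded event is 1/136 = 0.74 percentage points. At the 30 per sequence that the protocol needs before its dropout allowance, it is 1/(30 × 4) = 1/120 = 0.83 points. This shows what one event would weigh. It does not estimate how many there would be.

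**The case against.** The strongest reply is that the three criteria are sufficient conditions, not a closed test. A result that meets none of them can still be reported, the investigator decides, and an investigator worried enough to stop drug would ordinarily call the result clinically significant. This stands, and it limits the claim to results that can go unrecorded. It does not remove the point: the criteria exist to make that judgement consistent across sites, and they omit the dosing actions that would most directly signal significance.

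The second reply is that the criterion on further diagnostic work catches most cases. For transaminases this is right, since Protocol 11.7.7 requires a thorough search for causes. For QTcF it is partly right. Section 11.7.4 relies on repeat ECGs, but discontinuation may turn on whether another etiology is identified, and looking for one can reasonably count as further diagnostic work. What remains is mainly discretionary holds or stops for other asymptomatic results.

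Third, other records exist. Besides the outputs in Step 3, interruptions over 72 hours must be notified to the Medical Monitor (10.5), and separate AE eCRF guidelines and training are promised (11.7.1). Those guidelines are not available here and may already cover the case.

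A reader might go further and infer that results which stop treatment will routinely be lost, or that the loss flatters the active regimens. The documents support neither. They say that repeat testing does not necessarily qualify, which is weaker than excluding it. They give no rates of such abnormalities by treatment, and investigators apply the rule blinded.

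**Conclusion.** The third criterion in Protocol 13.1.1.2 conflicts with the protocol's own dosing rules and action categories. It names one action that cannot occur and another that is distinct from stopping drug, and it leaves out the two that can occur. Asymptomatic abnormalities that lead to a hold or stop with no work-up beyond repeat testing can therefore go unrecorded as AEs and be missing from the SAP's TEAE-based interruption and discontinuation outputs.

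This is a minor point. The exposed cases are few in kind, part of the information survives elsewhere, and the efficacy analyses do not use AE status. One event would weigh about 0.7 to 0.8 percentage points for a treatment, but the documents support neither a count of events nor a direction of bias. The conclusion rests on the protocol text alone and assumes that the separate eCRF completion guideline does not already close the gap.

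**What to change.** Reconcile Protocol 13.1.1.2 with 10.4 and Table 13-3 by rewording the third criterion as: *Interruption or permanent discontinuation of study drug, or discontinuation from the study*. Make the AE eCRF completion guideline say the same. The SAP needs no change, since its tables would pick up the added AEs as specified.

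The cost is one line of protocol text and the matching guideline entry; a few more AEs may be recorded. The change concerns AE reporting only. It does not touch when drug is held, stopped or resumed.
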